#### 9.3.1. MMRM

Primary treatment comparisons between Intepirdine and placebo will be performed on the change from Baseline to Week 24 using an MMRM with restricted maximum likelihood estimation, an unstructured covariance matrix, and the Kenward-Roger approximation for denominator degrees of freedom. The model will include terms for treatment, visit, treatment by

visit interaction, pooled geographic region, baseline MMSE score, the baseline value, and the baseline value by visit interaction.

- The region by treatment interaction term will be evaluated at the 10% level of significance; if the interaction term is found to be significant, it will be included in the MMRM model. Note, this applies to ALL MMRM models.
  - For the by-region Subgroup analyses, where, because the subgroup analyses by Region only include 1 region, the interaction makes no sense. The same MMRM model is also used for subgroups for the primary efficacy endpoint, as appropriate.

As additional supportive information, treatment differences at *each post baseline visit* will also be derived using the MMRM model; however, primary inferences will be drawn from treatment differences derived from the MMRM models at Week 24.

The estimated treatment difference (“Intepirdine 35mg – Placebo” and “Intepirdine 70mg – Placebo”) at each visit will be displayed in the summary of statistical analysis together with the 95% confidence interval and the associated p-value.

No imputation of the missing values will be performed for the primary analyses, ie, the data used in the analysis will be the actual observed responses at each visit.

Least Squares Means for each visit will also be presented with the standard error and the number of subjects contributing to the Least Squares Means. Least Squares Means and estimated treatment differences for each visit and the associated 95% confidence interval will be displayed graphically.

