#### **9.3.1.1. Further Details of the MMRM Analysis**

The mixed model for repeated measures (MMRM) model will be fitted using SAS PROC MIXED procedure with restricted maximum likelihood estimation, an unstructured covariance matrix, and the Kenward-Roger approximation for denominator degrees of freedom. The unstructured covariance is the least restrictive and generally performs well with limited number of repeated measures per patient and puts no parameters on the data with respect to the covariance structure assumptions.

- Only in the unlikely circumstance that there are convergence problems with the MMRM analysis will other covariance structures be examined to resolve the convergence issue, ie, we would evaluate other additional variance-covariance structures, including compound symmetry (CS), heterogeneous compound symmetry (CSH), and auto-regressive [AR(1)]. In this eventuality, the Akaike’s Information Criterion (AIC) will be used to determine the optimal variance-covariance structure matrix for the primary comparisons.
  - If convergence issues arise, the base by visit interaction may be dropped.

*Sample* SAS code is as follows. The actual SAS code may be modified as appropriate. Note that the treat\*region interaction will be assessed for significance (at alpha 0.10), and if not significant, will be dropped from the model.

```
ods trace on;
```

```
Proc mixed data=MMRM1 method=reml PLOTS (MAXPOINTS=200000000000);
  class usubjid trt avisitn region;
  model chg=trt avisitn trt*avisitn trt*region base basemmsescore
base*avisitn region /ddfm=kr;
  repeated avisitn/subject=usubjid type=un r;
  lsmeans trt*avisitn/pdiff cl ;
  lsmeans trt*region/pdiff alpha =0.10;
  ods output lsmeans=_LS diffs=_lsdiff tests3 =tst;
run;
ods trace off;
```

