#### **10.8.1. Falls as Reported from QSO**

The rate of falls per month will be analyzed using the data on fall occurrence that is collected at each visit in the Treatment Period via the Questionnaire for Signs of Potential Orthostasis.

Rate of falls per month = (total number of falls / duration (days)) x 30, where:

- Total number of falls = summation of falls over all visits in the Treatment Period (through Week 24)
- Duration of treatment (days) through Week 24 = (last dose date of double blind IP – first dose date of double blind IP) + 1

Incidence rate will be summarized by treatment. The incidence rate will be analyzed using the MMSE model methodology as described for the primary efficacy endpoint but without the ‘visit’ terms.

Additional analysis will be performed for each symptom by treatment, visit and overall

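### Falls per month are modelled as a normal outcome on individual rates, so a subject with three days of exposure weighs as much as one with 24 weeks

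*SAP*

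**What the plan says.** SAP 10.8.1 derives one value per subject from the orthostasis questionnaire: "Rate of falls per month = (total number of falls / duration (days)) x 30". The numerator is defined as "Total number of falls = summation of falls over all visits in the Treatment Period (through Week 24"). The denominator is days on double-blind drug, "last dose date of double blind IP – first dose date of double blind IP) + 1".

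For that value the plan is: "The incidence rate will be analyzed using the MMSE model methodology as described for the primary efficacy endpoint", with the visit terms left out. The SAP defines no MMSE model; MMSE is a cognitive scale that enters the efficacy models as a covariate. SAP 9.3.1 specifies the primary comparison "using an MMRM with restricted maximum likelihood estimation, an unstructured covariance matrix" and Kenward-Roger degrees of freedom. The sample code in SAP 9.3.1.1 ("model chg=trt avisitn trt*avisitn trt*region base basemmsescore" and further terms) has no weight statement and no exposure term.

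The safety analyses use the Safety Population, which requires only one double-blind dose (SAP 7.4). Protocol 6.6.2 asks for early stoppers to be recalled for an Early Termination Visit, and Protocol Table 2 schedules the questionnaire there. Short-exposure subjects can therefore contribute fall counts.

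**The concern.** A fall count is a small integer with many zeros and a long right tail. Dividing it by exposure gives a ratio whose variance depends strongly on how long the subject was observed. A linear model with constant variance ignores this: a rate estimated from three days gets the same weight as one estimated from 24 weeks.

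Falls matter in this population, and this is the only safety rate for which the SAP prescribes a model. Subjects with short exposure may have stopped because they fell. Their rates are then both the largest and the least reliable in the data set, and a handful of them can drive a between-arm difference and its interval in either direction.

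**Working it through.** **Reading of the model.** The main model for the primary endpoint is the MMRM. The LOCF ANCOVA in SAP 9.3.4.2 is also a normal linear model, so either reading of the misnamed model leads to the same place. With one row per subject and no visit terms, the MMRM is a linear regression with a single residual variance. Equal weighting follows because no weight or offset is given; the SAP does not state it in words.

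**Inputs.** From the documents: the rate formula (SAP 10.8.1), 24 weeks = 168 days, 80 per arm, two-sided 5%. The documents give no fall rate, dispersion or dropout, and no power for falls, so there is no stated figure to reproduce. All rates below are assumptions.

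**Step 1: one fall at different exposures.** Rate = 30 / days. Under a Poisson count the variance of a rate is proportional to 1 / days, so its ratio to that of a full-exposure subject is 168 / days.

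| Days | One fall, per month | Variance relative to 168 days |
|---|---|---|
| 3 | 10.0 | 56 |
| 7 | 4.29 | 24 |
| 14 | 2.14 | 12 |
| 28 | 1.07 | 6 |
| 84 | 0.357 | 2 |
| 168 | 0.179 | 1 |

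The 3-day and 168-day rates differ by 10 / 0.179 = 56-fold.

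**Step 2: effect on an arm mean.** Take 79 subjects with 168 days at 0.20 falls per month and one subject with 3 days and one fall.

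- Unweighted mean of individual rates: (79 × 0.20 + 10) / 80 = 0.3225, up 61%.
- Falls over person-time: falls = 79 × 5.6 × 0.20 + 1 = 89.48; months = (79 × 168 + 3) / 30 = 442.5; rate = 0.202, up 1%.

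**Step 3: weight under a count model.** With a log-exposure offset, the 3-day subject carries 3 / 168 = 1/56 of the weight of a full-exposure subject under Poisson. Under a negative binomial the weight is μ / (1 + αμ). With 0.20 per month and α = 1, μ = 1.12 gives 0.528 and μ = 0.02 gives 0.0196, a ratio of about 1/27.

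**Step 4: power when stopping is unrelated to falls.** 80 per arm, rate ratio 2, gamma shape 1, stopping uniform between days 3 and 167, 1,000 runs. The negative binomial dispersion was set to its true value, which favours that model slightly. Cells show linear model v negative binomial.

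| Placebo falls/month | 10% stop | 20% stop | 30% stop |
|---|---|---|---|
| 0.1 | 78% v 81% | 73% v 79% | 70% v 78% |
| 0.2 | 89% v 92% | 85% v 91% | 81% v 89% |
| 0.5 | 95% v 97% | 93% v 95% | 94% v 96% |

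The loss is 2 to 8 points. False rejection under equal rates was between 3.5% and 6.1% for both models. A second scenario (0.4 per month, dispersion 1.5, 15% leaving between days 3 and 59, 500 runs) gave 80% v 85% for a rate ratio of 2 and 70% v 74% for 1.75. Repeat runs gave 80–82% v 86–88% and 67% v 74–75%.

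**Step 5: stopping caused by falls.** Equal true fall rates in both arms, dispersion 1, 600 runs. Each fall led to stopping with probability 0.3 in one arm and 0.1 in the other.

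- At 0.2 per month the median ratio of mean individual rates was 1.52 (10th to 90th percentile 0.81 to 3.07). The negative binomial rate ratio was 0.99 (0.73 to 1.36).
- At 0.4 per month the medians were 1.53 and 1.01, with false rejection of 13% and 6%.
- A further set of runs gave about 1.5 with 10–12% false rejection for the linear model, and a negative binomial ratio of 0.93 to 0.95.
- With probability 0.1 in both arms at 0.2 per month, neither was biased, but the linear-model ratio spread from 0.58 to 1.72 against 0.76 to 1.36.

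**The case against.** The strongest reply is that the harm is limited. SAP 10 calls the safety analysis descriptive, Protocol 10.4.5.5 promises only incidence and descriptive summaries, and no falls hypothesis or decision rule exists. If stopping is unrelated to falls, the mean of individual rates is unbiased, type I error is near nominal, and only precision is lost. The 3-day example is rare: with 15% leaving between days 3 and 59 and 0.4 falls per month, the chance of exactly three days and a fall is about (0.15 / 57) × 0.04, or 1 in 10,000 subjects, which is under 1% of arms of 80. SAP 10.1 also compares the proportion falling by a CMH test and allows Kaplan-Meier and log-rank analyses, none of which a short-exposure rate can swamp.

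Most of this stands as a limit on severity. It does not rescue the method. The SAP prescribes a model for this rate, so the model should suit the data. The SAP 10.1 analyses use adverse-event falls rather than questionnaire counts, and the Kaplan-Meier part is optional. Exposures of one to four weeks are also distorted (Step 1), so the problem does not depend on the 3-day case. The doubt whether an offset model copes with fall-driven stopping is answered by Step 5: its ratio stayed between 0.93 and 1.01, against about 1.5.

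Two further points are fair. An offset does not repair mismatched windows or the count's recall period, and negative binomial fits can fail to converge. Both are taken up in the fix.

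**Conclusion.** The concern holds. As written, the falls rate is analysed by an equal-variance linear model on individual rates, with a 56-fold difference between two one-fall subjects at 3 and 168 days. The cost is modest when stopping is unrelated to falls (2 to 8 points of power in the main grid, type I error intact). It is material when falls lead to stopping at different rates by arm: a spurious ratio near 1.5 and false rejection of 10–13%. These sizes rest on assumed fall rates, dispersion and stopping patterns; the 56-fold arithmetic does not.

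The conclusion also rests on reading the MMSE model as the MMRM. If that reading is wrong, the model is undefined, which needs correcting too. Because this is an unpowered safety analysis with other falls summaries beside it, the change should be made before unblinding, but the trial's main conclusions do not depend on it.

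**What to change.** Replace the model sentence in SAP 10.8.1 with a negative binomial regression of each subject's total falls, with log(exposure days) as offset and terms for treatment, pooled region, baseline MMSE and AChEI use. AChEI use is a randomisation stratum (Protocol 7.2) and already appears in the falls CMH in SAP 10.1. Report rate ratios with 95% confidence intervals for each dose against placebo. Show total falls, person-time and falls per person-month by arm in place of the mean of individual rates. Name a fallback for non-convergence, for example Poisson regression with the same offset and robust standard errors.

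Three wording points belong in the same edit:

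- Correct the model name.
- Use one window for falls and exposure. SAP 7.7.2 runs the double-blind period to 7 days after the last dose, while the denominator stops at the last dose. A subject dosed for 3 days who falls during the next 7 scores 30 / 3 = 10 per month, against 30 / 10 = 3 on matched days.
- Correct the recall period for the number of episodes in SAP 10.8, which refers to the last minute and presumably means the last visit.

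The cost is SAP wording and one procedure call on data already collected. The downside is a possible convergence problem if falls are few, which the fallback covers.

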## **11. PHARMACOKINETIC ANALYSES**

Plasma intepirdine concentrations will be listed and summarized by treatment group and visit and included in the CSR.

Individual plasma intepirdine PK parameters ( $AUC_{\tau ss}$ ,  $C_{max-ss}$  and  $C_{min-ss}$ ) will be estimated from a prior population PK model developed from previously reported Phase 1, 2, and 3 studies. Model parameters will not be re-estimated with data from the current study, rather, individual PK parameters will be estimated using a post-hoc procedure. A report describing this procedure and listings and summaries of PK parameters will be included as an appendix to the CSR.

### **11.1. Pharmacokinetic/Pharmacodynamic analyses**

The relationship between intepirdine exposure and the primary endpoints of this study will be assessed graphically (scatter plot, linear or non-linear regression/smoothing lines). Namely, the relationship between individual intepirdine  $AUC_{\tau ss}$ ,  $C_{max-ss}$  and  $C_{min-ss}$  and the following:

- Change from baseline total score of the UPDRS Part III at Week 24
- Change from baseline total score of the ADAS Cog 11 at Week 24
- Total score of the CIBIC+ at Week 24

Additional linear/non-linear modeling of these endpoints may be performed based on these initial analyses. Additional modeling may be described in a separate SAP and report.

